#### 9.7.1.3 Subject Disposition

The number of subjects enrolled, prematurely discontinued from study treatment (defined as those who discontinued study treatment due to any reason except for progressive disease) and those with major protocol deviations will be counted. The reason for study drug discontinued will be summarized according to the categories in the CRF. The end of study status (alive, death, withdrew consent or lost to follow-up) at the data cutoff date will be summarized using the data from the survival follow-ups.

#### 9.7.1.4 Demographic and Other Baseline Characteristics

Demographic and other baseline characteristics for the FAS will be summarized using descriptive statistics. Continuous demographic and baseline variables include age, weight, and vital signs; categorical variables include sex, age group, ECOG performance status, race, and subtypes of nccRCC.

#### 9.7.1.5 Prior and Concomitant Therapy

All investigator terms for medications recorded in the CRF will be coded to an 11-digit code using the World Health Organization Drug Dictionary (WHO DD). The number

(percentage) of subjects who took prior and concomitant medications will be summarized on the FAS by Anatomical Therapeutic Chemical (ATC) class and WHO DD preferred term (PT). Prior medications will be defined as medications that stopped before the first dose of study drug. Concomitant medications will be defined as medications that (1) started before the first dose of study drug and were continuing at the time of the first dose of study drug, or (2) started on or after the date of the first dose of study drug up to 28 days after the subject's last dose. All medications will be presented in subject data listings.

#### 9.7.1.6 Efficacy Analyses

##### 9.7.1.6.1 PRIMARY EFFICACY ANALYSIS

Primary endpoint ORR assessed by investigator review will be analyzed using the Full Analysis Set. Subjects who did not have a tumor assessment for any reason will be considered as nonresponders and included in the denominator when calculating response rate.

In this population, ORR in the historical control is assumed to be 8% ([Hudes et al., 2007](#)). The ORR in this study is estimated as 25%, which is deemed a clinical meaningful improvement. Hence, the null and alternative hypotheses are set as follows:

$$H_0: \text{ORR} = 8\%$$

$$H_a: \text{ORR} \geq 25\%$$

Simon's Two-Stage Design ([Simon, 1989](#)) is used in hypothesis testing for the primary endpoints. The interim futility analysis after Stage 1 allows for an early evaluation of efficacy results in order to stop the study early in the case of low anticancer activity. A minimum of 2 responders as assessed by ORR in the Stage 1 subjects ( $n_1=16$ ) is required in the interim analysis for the study to proceed to Stage 2, in which 15 more subjects may be enrolled. In the final analysis of ORR, a minimum of 6 responders is required in Stages 1 and 2 subjects combined ( $n=31$ ) to claim the superiority of study treatment over historical controls.

The ORR based on investigator assessment in the final analysis will be calculated and a 2-sided Clopper–Pearson 95% confidence interval (CI) will be constructed.

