### **Efficacy Analyses**

#### Primary efficacy analyses

Primary endpoint ORR assessed by investigator review will be analyzed using the FAS. Subjects who did not have a tumor assessment for any reason will be considered as nonresponders and included in the denominator when calculating response rate.

In this population, ORR in the historical control is assumed to be 8% ([Hudes, et al., 2007](#)). The ORR in this study is estimated as 25%, which is deemed a clinical meaningful improvement. Hence, the null and alternative hypotheses are set as follows:

$$H_0: \text{ORR}=8\%$$

$$H_a: \text{ORR} \geq 25\%$$

Simon's Two-Stage Design ([Simon, 1989](#)) is used in hypothesis testing for the primary endpoints. The interim futility analysis after Stage 1 allows for an early evaluation of efficacy results in order to stop the study early in the case of low anticancer activity. A minimum of 2 responders as assessed by

ORR in the Stage 1 subjects ( $n_1=16$ ) is required in the interim analysis for the study to proceed to Stage 2 in which 15 more subjects may be enrolled. In the final analysis of ORR, a minimum of 6 responders is required in Stages 1 and 2 subjects combined ( $n=31$ ) to claim the superiority of study treatment over historical controls.

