## **9 INVESTIGATIONAL PLAN**

### **9.1 Overall Study Design and Plan**

E7080-M001-221 is a single-arm, multicenter, Phase 2 study of lenvatinib in combination with everolimus (lenvatinib 18 mg/day + everolimus 5 mg/day) in subjects with unresectable advanced or metastatic nccRCC who have not received any chemotherapy for advanced disease. A Simon's Two-Stage Design will be implemented in approximately 31 enrolled subjects. Sixteen subjects will be enrolled in Stage 1. If there are at least 2 responders as assessed by ORR, the study will proceed to Stage 2, in which 15 more subjects may be enrolled. Otherwise, the study will stop early for futility. In the final analysis of 31 subjects, at least 6 responders are required to show a statistically significant improvement of ORR over historical control in the same patient population.

This study consists of three Phases: a Pretreatment Phase (Screening and Baseline Periods), a Treatment Phase (starting Cycle 1, Day 1), and a Posttreatment Phase (End of Treatment Visit and survival Follow-up).

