### 9.7.2 Determination of Sample Size

The sample size is calculated using Simon's Two-Stage Design for the primary endpoint ORR assuming an ORR of 25% from this study versus an historical control of 8%. A total of approximately 31 subjects, including 16 in Stage 1, are planned to be enrolled in the study. The actual number of subjects accrued will depend on the results from Stage 1. If  $\leq 1$  responders are observed in the first 16 subjects treated (Stage 1), the enrollment will be stopped. The total sample size will be the actual number of subjects enrolled at the time of termination of the study. If  $\geq 2$  responders are observed in Stage 1, the study will proceed to Stage 2 and a total of 31 subjects will be enrolled. At least 6 responders in 31 subjects is required to claim superiority of the study treatment. This design yields a one-sided type I error of 0.0319 and the power of 0.8053 in Stages 1 and 2 combined.

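### Does the 2-sided 95% confidence interval for ORR contradict the rule that 6 responders in 31 subjects are enough to claim superiority?

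*Protocol*

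**What the plan says.** The decision on the primary endpoint is made by counting responders in a Simon two-stage design. Protocol sections 9.7.1.6.1 and 9.7.2 give the rule: Stage 1 enrols 16 subjects and needs at least 2 responders to continue. After 31 subjects, "At least 6 responders in 31 subjects is required to claim superiority of the study treatment". Table 6 gives the same two thresholds and nothing else. Section 9.1 describes the final threshold in the language of significance: "at least 6 responders are required to show a statistically significant improvement of ORR over historical control". Section 9.7.2 gives the operating characteristics: "This design yields a one-sided type I error of 0.0319 and the power of 0.8053 in Stages 1 and 2 combined".

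The interval comes in a separate closing sentence of section 9.7.1.6.1: the investigator-assessed ORR in the final analysis will be "calculated and a 2-sided Clopper–Pearson 95% confidence interval (CI) will be constructed". No sentence ties its lower limit to 8% or makes it a condition of success. The same 2-sided 95% level is used for PFS and OS (section 9.7.1.6.2) and for CBR and DCR (section 9.7.1.6.3).

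**The concern.** A test and a confidence interval for the same parameter are often read as two views of one result: the null is rejected exactly when the interval excludes it. That holds only if both use the same tail probability. Here the test has one-sided size 0.0319 and the interval has 0.025 in its lower tail. The mismatch shows at the smallest successful result: with 6 of 31 responders the report would claim a significant improvement over 8% and print an interval that begins below 8%. A reader who looks only at the interval could think that superiority had not been shown. The interval is also the ordinary binomial one and takes no account of the two-stage sampling.

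If the interval were a second success criterion, the stake would be real. The effective threshold would rise to 7 responders, and the stated power would no longer apply.

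**Working it through.** **Inputs (protocol sections 9.7.1.6.1 and 9.7.2).** Null ORR 8%; target ORR 25%; Stage 1 size 16, continue with at least 2 responders; total 31 (so 15 in Stage 2), reject with at least 6 responders; 2-sided 95% Clopper–Pearson interval.

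**1. The plan's own figures.** With X1 ~ Bin(16, p) and X2 ~ Bin(15, p), the probability of claiming superiority is

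P(claim; p) = Σ over x1 ≥ 2 of P(X1 = x1) × P(X2 ≥ 6 − x1).

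| | p = 8% | p = 25% |
|---|---|---|
| P(claim), computed | 0.03193 | 0.80534 |
| P(claim), stated | 0.0319 | 0.8053 |
| P(X1 ≤ 1), early stop, computed | 0.62985 | 0.06348 |
| Early stop, stated (section 9.7.3) | 0.6299 | 0.0635 |

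All four reproduce. The test has the size and power that the protocol gives.

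**2. The interval at and near the threshold.** The lower Clopper–Pearson limit L at x responders solves P(X ≥ x; n = 31, L) = 0.025. At x = 6, P(X ≥ 6; 31, 0.08) = 0.0339, which is above 0.025, so L must lie below 8%.

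| Responders | ORR | 95% limits | Excludes 8%? | Claim under the rule? |
|---|---|---|---|---|
| 5/31 | 16.1% | 5.45% to 33.73% | no | no |
| 6/31 | 19.4% | 7.45% to 37.47% | no | yes |
| 7/31 | 22.6% | 9.59% to 41.10% | yes | yes |

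The two outputs differ at 6/31 and at no other count.

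**3. How often that count occurs.** With a threshold of 7, P(claim) is 0.00966 at 8% and 0.67981 at 25%. Subtracting:

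- at 8%: 0.03193 − 0.00966 = 0.0223
- at 25%: 0.80534 − 0.67981 = 0.1255

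The 0.0223 is already inside the declared 0.0319. It is no extra error.

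**4. Is the planned interval valid after two-stage sampling?** Coverage was computed exactly over all outcomes of the design for true ORRs from 0.05% to 99.9% in steps of 0.05 percentage points. A trial that stops with 0 or 1 responder was given its interval on 16 subjects, the others on 31. The 95% Clopper–Pearson interval never falls below 95.0%; its minimum is 95.03%, near a true ORR of 30%. Ignoring the two stages does no harm to its coverage. The limit itself hardly moves either: solving P(claim; p) = 0.025 gives a design-adjusted lower limit of 7.56% at 6/31, against 7.45%.

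**5. Would another level be better?** A 2-sided 90% Clopper–Pearson interval agrees with the rule at n = 31: its lower limit is 8.78% at 6/31 and 6.58% at 5/31. But it corresponds to a nominal one-sided 0.05, which the protocol does not state. The level that matches the actual size, 1 − 2 × 0.0319 = 93.62%, still has a lower limit of 7.88% at 6/31. So 90% would be picked because it agrees. On the same two-stage outcomes its coverage falls to 89.6% near a true ORR of 27%, slightly under its nominal level.

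**The case for a change.** The best case for acting is this. The protocol itself fixes the count rule, the test size and the interval, so the mismatch cannot be put down to detail left for the SAP. It falls on the very count that defines success, which carries 0.0223/0.0319 = 70% of the type I error and 0.1255/0.8053 = 15.6% of the power. The amendment log says that independent imaging review was added with a possible regulatory submission in mind, so outside readers will see the interval. Choosing an interval after a 6/31 result would look post hoc, while a clarifying sentence now costs almost nothing.

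The arithmetic stands, and so does the fact that the protocol has no sentence on reading the interval beside the rule. The rest carries less weight than it seems. In a discrete test the critical value usually holds most of the rejection tail, so the 70% describes how a declared error rate is distributed and shows no flaw. The fall in power from 0.805 to 0.680 belongs to a threshold of 7, which the protocol does not use. The risk of a post hoc choice is absent, because both the rule and the interval are already fixed. Nor is it necessary to add that the count rule is the test: section 9.7.1.6.1, Table 6 and section 9.7.2 already say so.

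**Conclusion.** The concern does not hold. At 6/31 the report would make two true statements at two openly stated levels: the result meets a one-sided test of size 0.0319, and a 2-sided 95% interval runs from 7.45% to 37.47%. Neither is wrong, and only the first decides the trial. The discrepancy is confined to one count, with probability 0.1255 at a true ORR of 25% and 0.0223 at 8%, and the lower limit there misses 8% by 0.55 percentage points (8.00 − 7.45). The decision, the type I error of 0.0319, the power of 0.8053 and the sample size of 31 all stand. Adding a 90% interval would be a matter of presentation.

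This rests on two assumptions: that the final analysis has exactly 31 treated subjects, as the rule presumes, and that the interval stays descriptive, as the protocol has it. Were its lower limit made a criterion for success, the threshold would become 7 and the power 0.680, and the conclusion would change.

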**Table 6      Simon's Two-Stage Design for Interim Futility and Final Analyses of ORR**

	Threshold
Interim Analysis	Continue if $\geq 2$ responders when $n_1=16$
Final Analysis	Reject $H_0$ if $\geq 6$ responders when $n=31$

$H_0$  = null hypothesis,  $n$  = sample size for Stages 1 and 2 subjects combined,  $n_1$  = sample size for Stage 1 subjects, ORR = objective response rate

#### 9.7.1.6.2 SECONDARY EFFICACY ANALYSES

The PFS assessed by the investigator and OS will be analyzed using Kaplan–Meier product-limit estimates. Median PFS and OS and the cumulative probability of PFS at 3, 6, and 12 months and cumulative probability of OS at 6, 12, and 18 months will be presented with two-sided 95% CI if estimable. PFS censoring rules will follow [FDA Guidance for Industry, Clinical Trial Endpoints for the Approval of Cancer Drugs and Biologics \(2018\)](#).

The cumulative PFS and OS will be plotted over time. The median, first, and third quartiles from Kaplan–Meier estimation for PFS and OS will be provided with 95% CI if estimable.

#### 9.7.1.6.3 EXPLORATORY EFFICACY ANALYSES

The ORR based on IIR assessment will be evaluated using the same method described in the primary analysis.

A 2-sided Clopper–Pearson 95% CI will be constructed for CBR and DCR. The DOR and PFS per IIR assessment will be analyzed using time to event methods described above.

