#### Exploratory efficacy analyses

The ORR based on IIR assessment will be evaluated using the same method described in the primary analysis.

A 2-sided Clopper–Pearson 95% CI will be constructed for CBR and DCR. The DOR and PFS based on IIR assessment will be analyzed using time to event methods described above.

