#### 9.5.1.2.1 TUMOR ASSESSMENTS

Tumor assessments will be performed using RECIST v1.1. Investigator-determined response assessments are to be performed at the site by appropriately qualified personnel at each time point and recorded on the appropriate CRFs. Copies of all tumor assessment scans will be sent to an imaging core laboratory specified by the sponsor for quality assessment and independent imaging review. Tumor assessments will be carried out following the guidelines provided by the imaging core laboratory. Historical scans performed within the Screening period that do not follow the guidelines completely may be used to demonstrate eligibility, as long as they meet minimum standards as separately defined by the imaging core laboratory.

Tumor assessments including a CT chest and CT or MRI of the abdomen and pelvis, and other areas of known or newly suspected disease should be performed prior to Baseline (between Day -28 to Day -2) and every 8 weeks (within the 8th week) from the date of first dose during the Treatment Phase. The same imaging modality and image-acquisition protocol (including use or nonuse of contrast, oral and IV) should be used consistently across all time points. A brain scan will be performed at Screening, and thereafter if clinically indicated. Bone scans using whole body bone MRI, m-technetium (m-Tc) based bone scans, or F sodium fluoride positron-emission tomography (Na-F PET) will be performed during the pretreatment phase to establish a baseline (a historical bone scan performed within 6 weeks before first dose is acceptable), every 24 weeks, and as clinically indicated. Lesions identified on bone scans should be followed with cross-sectional imaging.

In subjects with complete response (CR) based on body CT/MRI scans, bone scan and brain scan, assessment will be required at response confirmation. All objective responses must be confirmed at least 28 days following the initial achievement of response. Subjects going off study treatments without disease progression in the Treatment Phase will continue to undergo tumor assessments according to the above schedule until disease progression is documented or another anticancer therapy is initiated.

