**Table 5 Schedule of Procedures/Assessments for Study E7080-M001-221**

Phase	Pretreatment a		Treatment b All cycles are 28 days in duration						Posttreatment c	
			Cycle 1		Cycle 2		Cycle 3 – Last Cycle			
Period	Screening	Baseline	Day 1 a	Day 8	Day 15	Day 1	Day 15	Day 1	End of Treatment	Follow-Up Period
Day	-21 to -2	-1	Day 1 a	Day 8	Day 15	Day 1	Day 15	Day 1	Within 30 days of last dose	Every 12 weeks d
Visit	1	2	3	4	5	6	7	8, 9, 10, etc.		
Amylase and Lipase	X	X				X		X	X	
Fasting lipids g	X	X						X	X	
TSH and free T4 levels r	X	X				X		X	X	
Urine dipstick testing s	X	X			X	X	X	X	X	
Pregnancy test t	X									
PK u			X		X	X		X		
Telephone contact										X d
Lenvatinib treatment			Once Daily							
Everolimus treatment			Once Daily							
Tumor assessments: CT/MRI v	X		Performed every 8 weeks after C1D1, or sooner if clinically indicated, until documentation of disease progression or beginning another anticancer therapy.							
Bone Scan w	X		Every 24 weeks $\pm$ 1 week after C1D1, or as clinically indicated. In subjects with CR based on body CT/MRI scans, a bone scan assessment will be required at response confirmation.							
Brain Scan x	X		If clinically indicated. In subjects with CR based on body CT/MRI scans, a brain scan will be required at response confirmation.							
Survival			Throughout							
Concomitant medications y			Throughout							
AEs/SAEs z			Throughout							

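### Scanning stops at what is in effect the investigator's progression call, so plain Kaplan-Meier for the exploratory IIR PFS and DOR is likely to be optimistic, and no planned analysis shows by how much

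*Protocol*

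**What the plan says.** Under 9.7.1.6.3, "The DOR and PFS per IIR assessment will be analyzed using time to event methods described above"; the Synopsis says the same ("The DOR and PFS based on IIR assessment will be analyzed using time to event methods described above"). The methods referred to are the Kaplan-Meier estimates of 9.7.1.6.2, where PFS censoring is set by reference to an FDA guidance whose text is not reproduced. No censoring rule is cited for DOR.

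On imaging, the tumor assessment row of Table 5 reads "Performed every 8 weeks after C1D1, or sooner if clinically indicated, until documentation of disease progression or beginning another anticancer therapy". For subjects who leave treatment without progression, 9.5.1.2.1 says they "will continue to undergo tumor assessments according to the above schedule until disease progression is documented or another anticancer therapy is initiated". Neither place names the assessor whose progression counts. However, 9.5.1.2.1 has the site determine response at every time point, and Appendix 1 gives the time-point determination to the investigator. The core laboratory receives copies of the scans for quality assessment and independent review.

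The only efficacy sensitivity analysis, in 9.7.1.6.5, repeats the analyses in the Evaluable Analysis Set.

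**The concern.** The investigator is the only reader described as acting at each visit, so it is the investigator's progression call that would end scanning. If the IIR later reads the same scan as not progressed, no further protocol scan exists to show when it would have seen progression. The subject then ordinarily leaves the IIR risk set as censored at that visit.

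Kaplan-Meier assumes that censored subjects have the same outlook as those who remain. Subjects whom the treating site has just judged to be worsening probably have a poorer one. If so, the IIR curve sits too high. Restricting to the Evaluable Analysis Set does not change this.

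According to the revision history, the IIR endpoints were added to support the investigator-assessed ones, with a possible regulatory submission of an open-label, single-arm study in view. An IIR PFS at or above the investigator's could be read as reassurance when part of the agreement comes from the scanning schedule. There is no control arm in which the same bias would cancel.

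**Working it through.** The plan gives no figure for IIR PFS or DOR, so there is none to reproduce on this point. Its one set of operating characteristics ("This design yields a one-sided type I error of 0.0319 and the power of 0.8053") reproduces exactly from the two-stage binomial (0.0319 and 0.8053). It rests on investigator ORR and is not touched here.

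**Inputs.** The 8-week scan interval comes from Table 5 and 9.5.1.2.1. Two inputs are assumptions:
- The true median PFS is 8 months, exponential. That is about 34.8 weeks at 4.35 weeks per month. The documents offer only 14.6 months, from an earlier RCC study (9.2).
- The IIR does not confirm a share d of investigator progressions at the scan concerned, with d = 10%, 20% or 30%.

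The model has one-way discordance and no separate deaths.

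**Formulas.** The chance of passing one 8-week interval without progression is s = 2^(−8/34.8) = 0.853, so q = 1 − s = 0.147. Six scans fall before week 52, the last at week 48.
- Investigator: s^6 = 0.384.
- IIR as planned: at each scan a fraction q(1 − d) of those at risk are events and qd are censored, so S = [1 − q(1 − d)]^6.
- IIR had scans continued, confirmed at the next scan: S = s^6 + d·q·s^5, with s^5 = 0.451.
- IIR had scans continued, each later scan again failing to confirm with probability d: S = s^6 + the sum over j = 1 to 6 of d^j·q·s^(6−j).

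| d | IIR as planned | Scans continued | Excess (points) |
|---|---|---|---|
| 10% | (1 − 0.133)^6 = 0.426 | 0.391 to 0.392 | about 3.4 to 3.5 |
| 20% | (1 − 0.118)^6 = 0.471 | 0.398 to 0.402 | about 7.0 to 7.4 |
| 30% | (1 − 0.103)^6 = 0.520 | 0.404 to 0.415 | about 10.6 to 11.6 |

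The median is a coarser measure because it moves in 8-week steps. At 20% it is 48 weeks as planned against 40 weeks with scans continued; at 10% it stays at 40 weeks.

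**Different discordance model.** Here the investigator calls progression one or two scans before the IIR would (simulation, true median 9 months). Twelve-month PFS rises from 0.40 to 0.43 at 10%, 0.46 to 0.47 at 20%, and 0.50 to 0.51 at 30%.

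**When the bias vanishes.** If unconfirmed calls are unrelated to prognosis (20% censored independently), the median is 9.05 against 9.06 months, so there is no bias.

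**Discordance in the other direction.** In the 8-month setting with 20% non-confirmation, suppose the IIR also calls 30% of progressions two scans before the site. The planned 12-month IIR PFS then falls from 47% to 44%. Its excess over the investigator's 38% drops from 47 − 38 = 9 points to 44 − 38 = 6.

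**The case against.** **It is SAP material.** The protocol defers detail to a SAP finalized before database lock, and a second Kaplan-Meier run and an agreement table could be written there. That is true of the remedy. But the missing scans follow from the protocol's own schedule, and the protocol itself fixes the method for IIR PFS and DOR by reusing the earlier one. The point concerns what is stated, not detail left out.

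**The premises are inferred.** No passage says whose progression ends scanning. Section 9.1.2 ends treatment at confirmed progression without naming who confirms, and the core laboratory's guidelines are not shown. This stands as a caveat. Still, no passage gives the IIR a role before scanning stops.

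**Censoring and deaths.** The cited guidance is not reproduced and survival follow-up continues, so a later death might count as an event. That could change the size. Such a death would come later than the unseen progression, so it would not by itself reverse the direction.

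**Size against precision.** With 31 subjects and 12-month PFS near 40%, the standard error is about √(0.40 × 0.60 / 31) = 0.088, or roughly ±17 points at 95%. This is wider than the illustrated shift. It limits the practical weight of the point, although a wide interval does not correct a systematic shift.

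**Reverse discordance.** It narrows the gap to the investigator's curve, as shown. It does not show that the bias is gone, because an IIR curve with continued scanning would be pulled down too.

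**Conclusion.** The point holds as an expected direction of bias in two exploratory endpoints. It rests on three assumptions: the investigator's call ends scanning, unconfirmed calls are ordinarily censored, and those calls carry prognostic information. Under the illustrative PFS model the 12-month excess is about 3, 7 and 10 to 12 points at 10%, 20% and 30% non-confirmation. These rates are assumed, not taken from the documents.

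A reader might infer more, and the documents do not support it:
- That IIR PFS will certainly exceed the investigator's. The rates are unknown, discordance can run both ways, and there is no bias if unconfirmed calls are uninformative.
- That the planned estimate is an upper bound. Nothing in the documents guarantees the direction, so likely optimistic is as far as one can go.
- That DOR is inflated by the same amount. No DOR calculation was made, and at the design ORR of 25% there would be only about 0.25 × 31 ≈ 8 responders.
- That independent review is left useless as a check. IIR ORR, the direct check on the primary endpoint, is not addressed by this point.

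The investigator ORR decision and investigator PFS are unaffected. This is a cheap improvement of low severity.

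**What to change.** In 9.7.1.6.3 and the matching Synopsis paragraph:
1. Keep the planned IIR PFS and DOR analyses, and describe them as likely optimistic where the investigator and the IIR disagree on progression.
2. Add a sensitivity analysis of each, with the event defined as the earliest of IIR progression, the investigator progression that ended scanning, or death.
3. Add a table of investigator and IIR agreement on progression, including timing, so that the actual discordance is visible.

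The cost is one more Kaplan-Meier run per endpoint and one table, with no additional scans. The drawback is that the sensitivity version brings investigator calls back into an endpoint meant to be independent. It should therefore be read as bracketing the IIR result, not replacing it.
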